BHL+PHN Condition. Participants randomized to the BHL+PHN condition were asked to participate in the same BHL classes and physical activity sessions as those in the BHL condition. Additionally, they were assigned to work one-on-one with a peer health navigator (African American with lived experience of mental illness) for eight months. Three peer health navigators were employed by HAH for Cohort 1 and Trilogy for Cohorts 2 and 3. One of the Trilogy peer health navigators vacated her position before the start of Cohort 3, leaving two of them to deliver the intervention at the end of the project. They received special manualized training from IIT research staff on how to provide support to study participants such as accompanying them to healthcare appointments, mental and physical health crisis management, trauma-informed care, harm reduction, and relapse management. Peer health navigators were also trained to assist participants with their diet and exercise goals. Activities to facilitate these

goals included accompanying them to food pantries and grocery stores to purchase nutritious food, meal planning and cooking, and engaging in physical activity out in the community.

Survey Assessments. Participants in all three conditions completed survey assessments at baseline, 4-month, 8-month, and 12-month study timepoints. Both intervention conditions lasted for a total of 8 months with the last survey assessment being indicative of a 4-month follow up. Surveys were completed through a technique called computer-assisted personal interviewing (CAPI), where research staff and participants work together to complete questionnaires face-to-face (Sainsbury et al., 1993). Research staff were trained and demonstrated CAPI performance to a criterion inter-rater reliability of .90 before conducting these survey assessments with participants independently. Survey assessments included a demographic questionnaire (baseline only) and measures related to self-report of various physical and mental health outcomes.

Monthly Check-In. Participants in all three conditions were asked to complete monthly check-ins throughout the 12-month duration of their involvement in the study. Monthly check-ins during baseline, 4-month, 8-month, and 12-month timepoints were administered at the same time as the survey assessments. All other monthly check-ins were administered over the phone by a member of the research staff.

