The monthly check-in was designed by the CBPR team as an assessment of diet and physical activity based on the healthy lifestyle behaviors included in the BHL curriculum and further promoted by peer health navigators. Participants were asked a total of 12 questions pertaining to diet, physical activity, and receiving support. Questions were answered on a 5-point scale (1=not at all [never], 5= most of the time [nearly every day]). For the purposes of this study, all twelve items were totaled to come up with a “Healthy Lifestyle Behaviors” score, with higher scores indicating greater frequency of behaviors. Next, the questions were divided into subscales with five items pertaining to physical activity and six items pertaining to diet. The five items pertaining to physical activity included: (Q1-3) How much did you participate in light /moderate /vigorous activities; (Q4) How much did you dance; and (Q5) How much did you walk up a flight of stairs? The six items pertaining to diet included: (Q7) How much did you eat a variety of foods from the 5 food groups; (Q8) How much did you eat only when you were hungry; (Q9) How much did you boil, steam, or bake your food instead of frying; (Q10) How much did you control your portion sizes; and (Q11-12) How much did you limit sugary drinks/fast food? The question regarding asking friends and family for support in health goals did not fall under the two subscales, but it was included in the total score.

Participant Compensation. All compensation was provided in the form of PNC Visa gift cards. Cohort 1 received \$25 per hour for completing survey assessments, \$10 for traveling to the assessment appointment, and \$10 for each monthly check-in. Starting with Cohort 2, compensation was decreased slightly; they received \$15 per hour for completing survey assessments, \$5 for traveling to the assessment appointment, and \$10 for each monthly check-in. For all three Cohorts, participants received an additional \$25 for bringing in the signed medical permission form.

A raffle and punch card system was designed to provide incentives for participation in the intervention. Participants from BHL or BHL+PHN conditions received a punch card and earned one punch for each BHL class or physical activity session they attended. Participants earned \$5 per punch for a chance to earn up to \$250. Participants could cash in for a \$50 gift card for every 10 punches.

COVID-19 Virtual Transition

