Participants were able to use their workbooks to follow along with class content and guided physical activity sessions over the phone. Low-impact exercises were written out and transcribed for BHL facilitators so that they could be delivered verbally. Peer health navigation activities were also transitioned to a telephonic format and included extra guided physical activity sessions, identifying physical activity opportunities that could be conducted from home or safely in the community, meal planning, setting up grocery delivery at home, or applying for additional resources such as free ride cards and food stamps. By June 2020, peer health navigators were encouraged to meet with interested participants face-to-face under the appropriate COVID-19 safety protocols (i.e., everyone must wear face masks covering the nose and mouth, keep 6 feet of distance, and use hand sanitizer) to provide the intervention whenever possible. BHL and BHL+PHN participants continued to receive virtual punches on their cards and all gift card payments were mailed to their home addresses.

Statistical Analysis Plan

Due to missing data, data analysis plan was revised from 3x4 and 3x13 ANOVAs to 3x2 ANOVAs (treatment groups X timepoints [baseline & 8-month]) for all intent-to-treat analyses, minimizing missing data, retaining power, maintaining intended plans to observe interventions from pre-test to post-test. Post-hoc comparisons were conducted as needed. As-treated analyses were conducted through 2x2x2 ANOVAs (treatment groups [BHL & BHL+PHN] X timepoints [baseline & 8-month] X attendance [yes or no, attended at least once]). If significant findings were observed, secondary analyses incorporated 4-month (mid-test) and 12-month interviews (follow-up) to determine if any changes occurred during these timepoints.

Originally, it was also proposed that a few intervention-related variables may be included as potential covariates in the analyses. These variables included: Study site where interventions were hosted (i.e., HAH or Trilogy), method of participant compensation (i.e., raffle or punch card), and format of interventions (i.e., in-person or online). As the addition of these covariates would only allow for conservative analyses without meaningful interpretation, potential cohort effects were not examined. Still, demographics would have been included as covariates if any differences were observed across treatment groups at baseline.

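### Nine of the 13 scheduled monthly check-ins enter no stated analysis; a likelihood-based model could use them and still keep month 8 as the target

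*Combined protocol and SAP*

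**What the plan says.** Under Study Procedures, Monthly Check-In: "Participants in all three conditions were asked to complete monthly check-ins throughout the 12-month duration of their involvement in the study". Four of these occasions coincide with the surveys: "Monthly check-ins during baseline, 4-month, 8-month, and 12-month timepoints were administered at the same time as the survey assessments". For the rest: "All other monthly check-ins were administered over the phone by a member of the research staff". The same section defines the outcome: "all twelve items were totaled to come up with a" Healthy Lifestyle Behaviors score, with a five-item activity subscale and a six-item diet subscale.

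The Statistical Analysis Plan then reports the change of method: "Due to missing data, data analysis plan was revised from 3x4 and 3x13 ANOVAs to 3x2 ANOVAs". It applies to every intent-to-treat analysis and compares baseline with month 8. The as-treated ANOVAs use the same two time points. Other occasions come in only if something is significant, and then "secondary analyses incorporated 4-month (mid-test) and 12-month interviews (follow-up) to determine if any changes occurred during these timepoints".

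The Missing Data paragraph fills missing items from up to two neighbouring values within the scale. The Drop-Outs paragraph says that people who left an intervention stay in the dataset if they completed any survey after baseline, with missing data filled by that same method.

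**The concern.** The check-in is the only measure described with 13 occasions, so the abandoned 3x13 ANOVA must refer to it. Under the revised plan its result rests on one post-baseline month out of 12. The occasions left out are exactly those collected separately from the survey visit.

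Two things are at stake. First, when a month-8 score is missing, the person's own months 6 and 7 would be the most informative data available, yet no stated method uses them. Second, retention in the dataset depends on completing a later survey. A participant who left an intervention, gave phone check-ins but completed no later survey would be omitted, although outcome data exist for that person. Both may cost precision and may make the analysed group more selected than it needs to be.

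**Working it through.** **Inputs from the documents.** Monthly check-ins for 12 months in all arms, with four tied to the survey (Monthly Check-In); analysis at baseline and month 8, months 4 and 12 conditional (Statistical Analysis Plan); target of 210, or 70 per arm (Recruitment); $10 per check-in (Participant Compensation). No missingness rate or within-person correlation is given, so those values below are assumptions.

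**1. Count.** Baseline plus months 1-12 gives 1 + 12 = 13 occasions, which reproduces the 13 in 3x13. Always analysed: 2. Conditionally analysed: 2 more. Never analysed: 13 - 4 = 9 (months 1, 2, 3, 5, 6, 7, 9, 10, 11), and 9/13 = 69%. Six of the nine fall within the eight-month intervention. The ceiling, at full enrolment and full completion, is 9 x 210 = 1,890 check-ins, or $18,900 in payments.

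**2. Does missing data justify dropping the 3x13 ANOVA?** Assume baseline is complete and each later occasion is missed independently with probability p. The expected number with complete data is 210(1 - p)^12 for 13 occasions and 210(1 - p) for two.

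| p | complete on 13 | complete on 2 |
|---|---|---|
| 0.05 | 113 | 200 |
| 0.10 | 59 | 189 |
| 0.20 | 14 | 168 |
| 0.30 | 3 | 147 |

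So leaving an ANOVA that needs all 13 values is reasonable. A likelihood-based model has no such requirement: each person contributes whatever was observed.

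**3. What such a model adds at month 8.** With a free mean for every arm and month, and full data, its estimate of change from baseline to month 8 equals that of the 3x2 ANOVA. The gain therefore comes from people who lack month 8 but have other months. Under the same independence assumption, month 8 is observed in 1 - p of participants, and at least one of months 6-8 in 1 - p^3:

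- p = 0.10: 90% and 99.9%
- p = 0.20: 80% and 99.2%
- p = 0.30: 70% and 97.3%

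These are coverage figures, not precision: month 7 carries only part of the information in month 8. The difference shrinks if people leave for good before month 6.

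**4. Mean of months 6-8 as a contrast.** Assume full data and equal variance (set to 1) at each occasion. The variance ratio is Var(mean of months 6-8 minus baseline) / Var(month 8 minus baseline).

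- Equal correlation, k months: (k + 1)/(2k) = 4/6 = 0.667 for k = 3, at any correlation.
- AR(1) with correlation r: [(3 + 4r + 2r^2)/9 + 1 - 2(r^6 + r^7 + r^8)/3] / [2(1 - r^8)].
 - r = 0.8: 1.405/1.664 = 0.844.
 - r = 0.9: 0.953/1.139 = 0.837.

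If the arm effect is the same in months 6, 7 and 8, relative efficiency is 1/ratio: 1.50, 1.18 and 1.19. If the effect grows linearly to month 8, the mean carries (6/8 + 7/8 + 8/8)/3 = 7/8 of it, and relative efficiency is (7/8)^2/ratio = 0.766/ratio:

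- equal correlation: 1.15
- AR(1) 0.8: 0.91
- AR(1) 0.9: 0.91

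**The case against.** The reduction is disclosed, with reasons. Month 8 is the end of both interventions, so baseline against month 8 is the natural before-and-after comparison. Before March 2020 those two occasions also shared the survey-visit setting, whereas months 6 and 7 were by phone. The check-in score is not named as primary, and the power statement concerns weight change. No bias is demonstrated.

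All of this stands. It supports month 8 as the target and rules out a months 6-8 average as the lead result. It does not explain why observed months should go unused when month 8 is missing. Nor does the two-point plan avoid the change of setting: under the COVID-19 Virtual Transition section, part of Cohort 2 at month 8, and Cohort 3 at every assessment after baseline, were by phone.

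A reader might also infer that anyone who missed month 8 disappears from the check-in analysis. The documents do not support that. The Drop-Outs paragraph retains intervention drop-outs who have any later survey and says their missing data are imputed. What is unclear is how within-scale neighbours can supply a score when the whole month-8 check-in is missing.

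**Conclusion.** The point holds as a matter of efficiency and use of data in one outcome family. Nine of 13 scheduled check-ins enter no stated analysis, and missing data does not require that. The benefit of using them for the month-8 contrast depends on how many people lack month 8 but have neighbouring months, which the documents do not reveal.

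Three stronger inferences should be resisted:

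- **That the missing data problem belongs to the ANOVA and not to the check-ins.** No rate is given for any month. The plan cites missing data in giving up the 3x13 analysis, so sparse phone check-ins fit the text equally well. Participants were asked for 13 check-ins; the documents do not say that 13 were obtained.
- **That averaging months 6-8 is worth roughly 20% to 50% more participants at no cost.** That needs full data and an equal arm effect in the three months. If the effect builds linearly, the result runs from a 9% loss to a 15% gain.
- **That a missed survey necessarily loses that month's check-in.** The text says the two were given together. It does not say that a separate call was ruled out.

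**What to change.** For the check-in total and its two subscales only, replace the 3x2 ANOVA with one likelihood-based repeated-measures model on all observed check-ins. Include arm, month as a category, arm-by-month and a stated within-person correlation structure, and include everyone with any check-in. An unstructured matrix for 13 occasions has 13 x 14/2 = 91 parameters, so name a simpler fallback before fitting.

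Keep the arm contrast in change from baseline to month 8 as the lead result. The mean of months 6-8 may be shown beside it as supportive, with its dependence on a similar effect across those months stated. Report the number of check-ins observed by arm and month, and say how a wholly missing month-8 score was handled in the ANOVA.

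The document is written in the past tense, so the new analysis cannot be presented as fixed in advance. Label it as added after the missing data were seen. Collecting missed month-8 check-ins by a separate call is no longer an option.

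The cost is a little more analysis work on data already collected, and reliance on a missing-at-random assumption. Before March 2020 there is also a phone versus survey-visit difference between months. It is the same in all arms at each month, so the arm contrast is protected unless the mode effect differs by arm.

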Peer Navigators to Address Obesity-Related Concerns for African Americans With Serious
Mental Illness

NCT03382782

11/29/2018

Study Protocol

CBPR Team Program Development

A CBPR team, comprised of key research staff from IIT (e.g., principal investigator, co-investigator, project manager, research assistant), one service provider, and six African Americans with serious mental illness, was convened at the beginning of the study. Team members worked together over the first 18 months to design a manualized diet and exercise program to address issues of weight management and physical activity among African Americans with serious mental illness. They conducted qualitative research to adapt an existing MOVE! Manual developed by the Department of Veterans Affairs National Center for Health Promotion and Disease Prevention (Goldberg et al., 2013; U.S. Department of Veterans Affairs, 2012). The resulting adaptation was called Behaviors for Healthy Lifestyles (BHL). The team also adapted an existing peer health navigation (PHN) manual utilized in prior research involving African Americans with mental illness who were homeless (Corrigan et al., 2017) and Latinx with serious mental illness (Corrigan et al., 2018) to address the healthy living goals of the current project. The CBPR team met when needed to provide additional guidance across the three study cohorts. This included assisting with recruitment, making decisions for participant compensation and incentives, and revising the curriculum into a virtual format during the COVID-19 pandemic.

Study Design

This study was a three-arm randomized controlled trial: (1) Integrated Care-Treatment as Usual (IC-TAU), (2) Behaviors for Healthy Lifestyles (BHL), or (3) Behaviors for Healthy Lifestyles plus Peer Health Navigation (BHL+PHN). Data were collected across three 12-month cohorts with survey assessments conducted at baseline, 4-month, 8-month, and 12-month timepoints along with monthly check in calls.

Recruitment

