IIT research staff guided all potential participants through an informed consent process prior to starting the baseline survey assessment. The informed consent included five key sections: (1) purpose of the study, (2) groups and requirements of the study, (3) risks, (4) benefits, and (5) compensation. Participants were also provided with the number for a psychologist to talk to, free of charge, to discuss any feelings related to participating in the study, or their rights as a participant.

Release of Information.

Individuals entering the study during Cohorts 2 and 3 with Trilogy were asked to sign a release of information form. The form was required so that the IIT research team could release relevant contact information to Trilogy for the purposes of informing them of the participant’s assignment to one of the intervention conditions, confirming insurance eligibility, and scheduling

an intake meeting. Participants were not allowed to begin the intervention until Trilogy staff completed their intakes and registered them as existing clients within the organization.

Study Procedures

Once individuals were determined to be fully eligible and completed all necessary documentation, they were enrolled as research participants into a designated cohort and randomized to one of three study conditions for a period of 12 months. Cohort enrollment periods appear to be longer than twelve months because participants completed their baseline in sections: Cohort 1 sections were enrolled from December 2017 through March 2019. Cohort 2 sections were enrolled from January 2019 through August 2020; and Cohort 3 sections were enrolled from December 2019 through February 2021.

Randomization.

This study utilized stratified block randomization by gender. IIT research staff picked up an envelope labeled either “female” or “male” for the participant’s identified gender, and blindly chose one of three cards at random which indicated the assigned research condition. Participants were randomized to either Integrated Care-Treatment as Usual (IC-TAU), Behaviors for Healthy Lifestyles (BHL), or Behaviors for Healthy Lifestyles plus Peer Health Navigation (BHL+PHN).

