Beginning in March 2020, all study activities were transitioned to a virtual format due to public health concerns and restrictions presented by the COVID-19 pandemic. This included the last portion of 8-month assessments and all 12-month assessments for Cohort 2 as well as all assessments following baseline for Cohort 3. IIT research staff conducted all survey assessments and monthly check-ins over the phone with participants. Participants were sent a copy of the answer choices to help them follow along. All gift card payments were mailed to their home addresses.

From March 2020 through October 2020, IIT and Trilogy staff met weekly to help BHL facilitators and peer health navigators transition to virtual services and monitor activities during the remainder of the 8-month intervention period for Cohort 3. Participants in BHL or BHL+PHN conditions were transitioned to individualized, telephonic services instead of group classes as follows:

- BHL Condition
 - 1-hour total
 - Cover class content and worksheets for the first 30-40 minutes
 - Offer short guided physical activity over the phone after content is complete
- BHL+PHN Condition
 - 1.5-hours total
 - Cover class content and worksheets for the first 30-40 minutes
 - Immediately before or after the individual course portion, engage in peer health navigation—this may include physical activity
 - As always, peer health navigation should apply lessons from the class and work toward the participants' weekly healthy living goals
 - Peer health navigation should be a distinct activity from the course content

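### The intent-to-treat test was changed to a baseline/8-month 3x2 ANOVA because of missing data, with no usable date for the change, and the planned 3x4 and 3x13 comparisons are no longer reported unconditionally

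*Combined protocol and SAP*

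**What the plan says.** The Study Design section sets out "survey assessments conducted at baseline, 4-month, 8-month, and 12-month timepoints along with monthly check in calls".

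The Statistical Analysis Plan opens with the change: "Due to missing data, data analysis plan was revised from 3x4 and 3x13 ANOVAs to 3x2 ANOVAs". The new test is defined by two timepoints and applies throughout ("treatment groups X timepoints [baseline & 8-month]) for all intent-to-treat analyses"). The reasons offered are "minimizing missing data, retaining power, maintaining intended plans to observe interventions from pre-test to post-test".

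Other survey visits come in by one route only: "If significant findings were observed, secondary analyses incorporated 4-month (mid-test) and 12-month interviews (follow-up"). No analysis of the full series of monthly check-ins remains.

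On baseline balance, the same section says that "demographics would have been included as covariates if any differences were observed across treatment groups at baseline".

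The cover carries the date 11/29/2018. Study Procedures states that "Cohort 3 sections were enrolled from December 2019 through February 2021", and the COVID-19 section states "Beginning in March 2020, all study activities were transitioned to a virtual format".

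**The concern.** A test chosen once data are in hand keeps its nominal 5% error only if the choice did not depend on the outcome comparison. To judge that, a reader needs the date of the choice and what was known then. The plan gives neither, and the one date on the document is incompatible with its content.

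The revision also narrows what will be shown. If the 3x2 is not significant, the plan calls for no analysis of the 4- and 12-month surveys. If it is significant, they enter as secondary analyses. In neither case is the planned group-by-time comparison set beside the 3x2, so nobody can see whether the two agree. At stake is whether a significant 3x2 result is read as confirmatory, and whether a null one hides a pattern at other visits.

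**Working it through.** **1. Dates.** From November 2018 to March 2020 (virtual transition) is 16 calendar months, and to February 2021 (end of the stated Cohort 3 period) is 27. Cohort 2 enrolment began in January 2019 and Cohort 3 in December 2019, both after the cover date. The analysis section is itself in the past tense. The present text was not written on the cover date, so that date says nothing about when the 3x2 was chosen.

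**2. What had been seen.** Missingness certainly had, since it is the stated reason. The sentence on demographics implies that baseline characteristics had been compared by arm. No sentence says that outcomes by arm had, or had not, been examined.

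**3. What the revision leaves out.** There are four survey visits, matching the 4 in 3x4. Baseline plus 12 monthly check-ins gives 13, matching 3x13 (my inference).
- Surveys: the 3x2 uses 2 of 4 visits. The other 2 depend on significance.
- Check-ins: if the 3x2 is applied to them, it uses 2 of 13. Even if the 4- and 12-month points are admitted, 13 − 4 = 9 check-ins have no analysis.

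**4. Type I error from choosing between tests.** Inputs: 70 per arm (Recruitment section). Assumptions: no true effect, complete data, equal correlation of .5 to .8 between visits, 5% level. Each test alone rejects in about 5% of simulated trials. The proportion in which at least one of the two has p < .05 is:

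| Pair of tests | Either p < .05 |
|---|---|
| 3x4 and 3x2 | 7.9% to 8.6% |
| 3x13 and 3x2 | 8.9% to 9.9% |

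Two independent tests would give 1 − 0.95² = 9.75%, so the top of the second range includes simulation error. These are ceilings, reached only if the better p-value decided the choice. If missingness alone decided it, the excess is zero.

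**5. The power statement.** The plan's only design figure is 81% power with 210 participants. It cannot be reproduced from what is stated, because the model, within-person correlation, alpha and dropout are not given. Taking arm means 0, −.07 and −.20 (0 for usual care is assumed), the overall mean is −.09, and the three-group noncentrality is 70 × (.09² + .02² + .11²) = 70 × .0206 = 1.442. That gives 17% power. On change scores the noncentrality becomes 1.442 / [2(1 − ρ)], and 81% requires ρ of about .93: 1.442 / .144 = 10.0. The figure is thus reachable under unstated assumptions and is not shown to be wrong. At that ρ, assumed attrition of 10, 20, 30 and 40% leaves 76, 71, 65 and 57% power on complete cases. The plan reports no amount of missing data, so its claim that the 3x2 retains power cannot be checked.

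**6. Imputation.** The Drop-Outs paragraph imputes missing data for people with at least one later survey, by the method given for items within a scale. If this covers whole missed visits, missing data alone does not explain leaving the 3x4. If it covers only items, the 3x2 still loses everyone without an 8-month survey. On either reading the numbers analysed by arm and visit are needed.

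**The case against.** The case for the plan is substantial. It names the original tests, the replacement and the reason. Eight months is the end of the intervention, so baseline to 8 months is the natural contrast. Checking for missing values before any analysis, as the plan describes, fits a choice made without sight of outcomes. All of this stands, and it rules out several stronger readings that a reader might infer:

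- *That a post hoc test is passed off as pre-specified.* The plan's own sentence says it was revised. Only the cover date could mislead.
- *That outcomes by arm guided the choice.* Only missingness is shown to have been seen. The demographics sentence concerns baseline characteristics.
- *That the planned tests were run and withheld.* The document contains no results. It shows only that they are no longer in the intent-to-treat plan.
- *That the plan claims to be unchanged.* The words about intended plans refer to the pre-test to post-test aim.

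It is also fair to say that rerunning the 3x4 on complete cases would be a poor arbiter, because it has fewer people and tests a broader hypothesis. As an illustration, take a 3x2 with 56 per arm and 80% power (noncentrality 9.81), and assume half the 8-month effect is present at month 4. With 42 complete cases per arm, the 3x4 has noncentrality 9.81 × (42/56) × (.6875/.5) = 10.1 and 64% power if the full effect persists to month 12. If half fades by then, it is 9.81 × (42/56) × (.5/.5) = 7.36 and 48%. Here .6875 and .5 are the sums of squares about the mean of the profiles (0, .5, 1, 1) and (0, .5, 1, .5), and the dividing .5 is that of (0, 1). Non-significance of the planned test should therefore not by itself downgrade a 3x2 result.

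This argues for a better method of reporting the planned comparison, not for leaving it out. Disclosing a change without its timing or what was known does not show that it was independent of results.

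**Conclusion.** The point holds in a limited form. The intent-to-treat test was changed because of observed missing data. The change is disclosed but undated, sight of outcomes by arm is not addressed, and the cover date cannot support pre-specification. The planned four-visit comparison survives only in part and only after significance, and the 13-point comparison has no replacement. The possible inflation runs from none (choice on missingness alone) to about 8 to 10% per outcome (choice on results), under the assumptions in the working. The documents do not place the trial within that range. The practical loss is that a reader cannot see whether the conclusion depends on the revision.

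**What to change.** In the Statistical Analysis Plan:

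1. For every outcome, report the originally planned group-by-time comparison (four survey visits, 13 check-ins) beside the 3x2, whatever the 3x2 shows. Fit it as a likelihood-based mixed model on all available visits, so that complete-case loss does not recur, and give numbers analysed by arm and visit.
2. Label the 3x2 tests, and the 2x2x2 as-treated tests on the same two timepoints, as a post hoc revision. State when it was made and what had been seen by arm at that time.
3. Report and discuss any disagreement between the two analyses, without a rule that downgrades a 3x2 result only because the planned comparison is not significant.
4. Correct the document date so that it does not precede the content.

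The cost is some wording and one further set of models on data already collected. The downside is that results may look mixed. This is a cheap improvement.
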